9.2.2. Sample Size for Phase 1 (Part 2)

Once an INCAGN01876 dose cohort in Treatment Group A is deemed tolerable, up to 6 evaluable subjects will be enrolled in Treatment Group B at the same dose of INCAGN01876. For example, if 3 mg/kg of INCAGN01876 is tolerated in Treatment Group A, then 3.0 mg/kg will be explored in up to 6 evaluable subjects in Treatment Group B.

9.2.3. Sample Size for Phase 2

Phase 2 will further evaluate the safety, tolerability, preliminary efficacy, [REDACTED] of the immune therapy combinations as part of dose expansion cohorts in Treatment Groups C and D. In Phase 2, a Simon 2-stage design will be run for each tumor type within a given treatment group.

The sample size for each tumor type within a given treatment group will be guided by the Simon 2-stage design. The planned Simon 2-stage designs are summarized in [Table 21](#). Each Simon 2-stage design will have a stopping rule to allow early termination of a particular cohort at the end of Stage 1 if there are insufficient responses observed, while enrolling enough subjects to predict possible target responses worthy of cohort expansion and potentially further evaluation in future studies.

The individual Simon 2-stage designs run for each tumor type within each treatment group will have design parameters that are determined by historical response rates. For the RCC and UC cohorts, the insufficient response rates are obtained from historical data, and the Simon 2-stage designs allowing early termination are based on ORR. For the melanoma cohort, the insufficient response rate is obtained from historical data, and the primary endpoint for the Simon 2-stage design allows for early termination based on CRR. The same Simon 2-stage design parameters will be used for the alternative dosing sequences represented by Treatment Groups C and D in

the same tumor type. For example, the RCC cohorts in Treatment Groups C and D will use the same Simon 2-stage parameters.

In order to determine whether the target response rate ($p_1\%$) is likely, an initial number of evaluable subjects (n_1 subjects) will be treated at the MTD [REDACTED] and schedule of INCAGN01876 within the corresponding tumor type and treatment group and will be enrolled in a cohort (Stage 1). If there are r_1 or fewer responses in the cohort, it will be concluded that the true response rate is unlikely to be greater than or equal to the target rate, and no more subjects will be enrolled in that tumor type cohort for that treatment group in Stage 2. In the cohorts in which greater than r_1 responses are observed among the Stage 1 subjects, n_2 additional evaluable subjects will be treated in Stage 2 to estimate the response rate. At the end of Stage 2, if $\leq r$ subjects have responded among the n evaluable subjects, the triplet combination dosing sequence will be declared nonpromising for that cohort. In other words, after the study is finished, if there is a sufficient number of responses in the 2 stages combined, the triplet combination dosing sequence is considered promising; otherwise it is considered nonpromising. The detailed calculations for each tumor-specific cohort are based on a 1-sided Type I error of 0.05 and power of 85%. The individual p_0 and p_1 values for the tumor types are listed in [Table 21](#).

A second approach to determining whether the treatment is active across the cohorts will use an integrated Bayesian futility analysis of tumor and dosing strategies specific to Treatment Groups C and D (see [Section 9.6.2](#)).

Formal quarterly safety reviews will be conducted to review efficacy and safety data with the obligation to hold a safety review meeting every 6 months.

[figure not shown]

Table 21: Planned Simon 2-Stage Designs for Phase 2

Indication	Combination	r_1	n_1	r	n_2	n	p_0	p_1
Melanoma (CRR)	GITR + Pembro + Epcadostat	6	21	18	31	52	26%	45%
RCC (ORR)	GITR + Pembro + Epcadostat	8	19	25	31	50	40%	60%
UC (ORR)	GITR + Pembro + Epcadostat	3	10	14	24	34	30%	55%

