1.5. Study Rationale

1.5.1. Rationale for the Study Population

Most cancers exhibit genetic heterogeneity, which often translates into enhanced tumor immunogenicity. This concept of tumor immunogenicity is well-appreciated for its role in eliciting an adaptive immune response and determining the efficacy of immunotherapy. Blockade of PD-1/PD-L1 has led to clinical responses in patients with many different types of cancer, including melanoma, NSCLC, RCC, SCCHN, gastric cancer, HCC, TNBC, cervical cancer, and bladder ([Hamid et al 2013](#), [Powels et al 2014](#), [Topalian et al 2014](#), [Brahmer et al 2015](#), [Dirix et al 2015](#), [Ferris et al 2016](#), [Frenel et al 2016](#), [Herbst et al 2016](#), [Le et al 2016](#), [Melero et al 2016](#), [Rosenberg et al 2016](#)). The combination of pembrolizumab and epacadostat has also demonstrated improved ORR compared with monotherapy PD-1/PD-L1 in a variety of tumor types, including melanoma, NSCLC, RCC, SCCHN, and UC ([Gangadhar et al 2017](#), [Lara et al 2017](#), [Hamid et al 2017a](#), [Smith et al 2017](#)); however, further clinical improvement is warranted.

The Phase 2 portion of this study (INCAGN 1876-202) will utilize a Simon 2-stage design to evaluate the benefit of the combination of pembrolizumab, epacadostat, and INCAGN01876 ([Simon 1989](#)). The approximate number of subjects for Stage 1 and Stage 2 for each treatment group and tumor type was determined based on an observed improvement in the ORR from the INCB 24360-202 study, as outlined below.

Epacadostat and Pembrolizumab in Melanoma

Preliminary efficacy results for subjects with melanoma enrolled in the Phase 1 portion of Study INCB 24360-202 was presented at the 2016 European Society for Medical Oncology annual meeting ([Gangadhar et al 2016](#)). Twenty-two subjects with advanced melanoma were enrolled in Phase 1; of the 19 treatment-naïve melanoma subjects, 11 subjects (58%) achieved an objective response (CR or PR) by RECIST v1.1, with 5 of 19 subjects (26%) achieving a CR. [REDACTED]. The combination of INCAGN01876, pembrolizumab, and epacadostat will be evaluated to determine if the combination regimen can improve the CRR of 26% in this setting.

Epacadostat and Pembrolizumab in Renal Cell Carcinoma

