Subjects with RCC enrolled in the INCB 24360-202 study showed improved ORR and DCR compared with pembrolizumab monotherapy. Of 30 efficacy-evaluable subjects, 63% (n = 19) had 0 to 1 prior line of therapy, and 37% (n = 11) had ≥ 2 prior lines of therapy for advanced disease. The ORR (CR + PR) and DCR (CR + PR + SD) for subjects with 0 to 1 prior line of therapy were 47% (9/19; 1 CR, 8 PR) and 58% (11/19; 1 CR, 8 PR, 2 SD), respectively. For subjects with ≥ 2 prior lines of therapy, ORR and DCR were 0% and 36% (4/11; all SD), respectively. At the time of the data cutoff, 9/9 responses were ongoing (range, 1+ to 372+ days; [Lara et al 2017](#)).

Epacadostat and Pembrolizumab in Urothelial Carcinoma

Responses by RECIST v1.1 were also observed in subjects with UC enrolled in the INCB 24360-202 study. In the UC group, a total of 37 subjects were considered efficacy evaluable. Preliminary ORR (CR + PR) and DCR (CR + PR + SD) for all urothelial efficacy-evaluable subjects were 35% (13/37; all PR) and 57% (21/37; 13 PR, 8 SD), respectively. At the time of the data cutoff, 12/13 responses were ongoing (range, 1+ to 652+ days; [Smith et al 2017](#)).

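### Should the plan have named a source for the insufficient response rates of 40% (RCC) and 30% (UC)?

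*Protocol*

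**What the plan says.** Two parts of the protocol describe where the Phase 2 inputs come from. Section 1.5.1 says that the number of subjects per stage, treatment group and tumor type "was determined based on an observed improvement in the ORR from the INCB 24360-202 study, as outlined below". That study tested pembrolizumab plus epacadostat. The paragraphs that follow report its results in melanoma, RCC and UC. For melanoma they also state the aim: the triplet "will be evaluated to determine if the combination regimen can improve the CRR of 26% in this setting". The RCC and UC paragraphs contain no such sentence.

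Section 9.2.3 says "For the RCC and UC cohorts, the insufficient response rates are obtained from historical data" and describes the melanoma rate in the same way. The Synopsis and SAP Section 3.4.3 repeat this. Protocol Table 21 and SAP Table 6 then list an insufficient rate p0 and a target rate p1 of 26% and 45% for melanoma (CRR), 40% and 60% for RCC (ORR), and 30% and 55% for UC (ORR). Neither document attaches a study, population or line of therapy to the 40% or the 30%.

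**The concern.** A reader who follows Section 1.5.1 expects all three null rates to come from the doublet study. Melanoma fits: 5 of 19 is 26%. RCC and UC do not, and both tabled rates are below the doublet ORR nearest to the enrolled population.

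The gap seems to matter because the doublet is the background to which INCAGN01876 is added. Section 1.5.1 says the doublet "has also demonstrated improved ORR compared with monotherapy PD-1/PD-L1 in a variety of tumor types, including melanoma, NSCLC, RCC, SCCHN, and UC" and adds: "however, further clinical improvement is warranted". Section 9.6.2 builds its Bayesian priors from the same p0 and p1 to judge whether INCAGN01876 is active. If p0 is below what the doublet achieves alone, the 0.05 error does not limit the chance of crediting INCAGN01876 with the doublet's own effect.

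**Working it through.** **1. Reproduce the tabled designs.** The inputs are r1, n1, r, n, p0 and p1 from Table 21, with n2 = n − n1. The probability of calling a cohort promising at true rate p is

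P(promising | p) = Σ over x from r1+1 to n1 of Bin(x; n1, p) × P[Bin(n2, p) > r − x].

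| Cohort | r1/n1 | r/n | p0 | p1 | P(promising) at p0 | P(promising) at p1 | P(stop after Stage 1) at p0 |
|---|---|---|---|---|---|---|---|
| Melanoma | 6/21 | 18/52 | 26% | 45% | 0.0496 | 0.855 | 0.707 |
| RCC | 8/19 | 25/50 | 40% | 60% | 0.0483 | 0.851 | 0.667 |
| UC | 3/10 | 14/34 | 30% | 55% | 0.0456 | 0.853 | 0.650 |

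A full search for the design with the smallest expected size at p0, subject to error ≤ 0.05 and power ≥ 0.85, returns exactly these three rows. The totals also agree with Protocol Section 4.3.1: Stage 1 is 2 × (21 + 19 + 10) = 100 and Stage 2 is 2 × (31 + 31 + 24) = 172. The arithmetic is sound, and the sizes follow from the tabled p0 and p1.

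**2. Compare p0 with the rates in Section 1.5.1.**

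| Cohort | Reported for the doublet | p0 |
|---|---|---|
| Melanoma | CRR 5/19 = 26.3%; ORR 11/19 = 57.9% | 26% |
| RCC | 0 to 1 prior line 9/19 = 47.4%; 2 or more lines 0/11; pooled (9 + 0)/(19 + 11) = 9/30 = 30.0% | 40% |
| UC | all evaluable subjects 13/37 = 35.1% | 30% |

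No reported or pooled rate equals 40% for RCC or 30% for UC. The gaps are 47 − 40 = 7 points and 35 − 30 = 5 points. The melanoma match is with the CRR, whereas the sentence in Section 1.5.1 speaks of ORR. Read literally, that sentence does not produce the melanoma p0 either.

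**3. Precision of the reported rates.** The exact (Clopper-Pearson) 95% limits are the 0.025 quantile of Beta(x, n − x + 1) and the 0.975 quantile of Beta(x + 1, n − x).

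- RCC 9/19: 24.4% to 71.1%, which contains 40%.
- RCC pooled 9/30: 14.7% to 49.4%, which contains 40%.
- UC 13/37: 20.2% to 52.5%, which contains 30%.

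**4. What the difference could do.** Put other true rates into the formula of step 1 with the tabled boundaries:

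- RCC at 47%: 0.247 (0.263 at exactly 9/19).
- RCC at the pooled 30%: 0.0008.
- UC at 35%: 0.142 (0.146 at exactly 13/37).

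These are for the Simon rule alone. The Bayesian suspension in Section 9.6.2 could only lower them. By how much cannot be calculated, because the prior is not given.

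**5. What is still to be analyzed.** SAP Section 10.1.1.2 records limited enrollment in Treatment Group C and none in Groups B and D. SAP Section 9 drops the interim analyses, and Section 10.1.4 drops the Simon design with its Bayesian futility analysis. Sections 7.1 and 10.1.2 keep only a summary of ORR per RECIST v1.1. None of these outputs uses p0.

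**The case for a change.** The best argument for acting is that the doublet is the reference the plan itself has in mind. The Synopsis describes the Bayesian rule as ending a cohort that is unlikely to improve on the background therapy, and that therapy is pembrolizumab plus epacadostat. The pooled RCC rate of 30% does not explain the lower null: it is not 40%, and it includes 11 subjects with two or more prior lines, whereas inclusion criterion 6b asks for no prior therapy for advanced disease. Nothing is blacked out in the RCC and UC paragraphs, so redaction does not account for the missing source. SAP Table 6 still prints the designs, SAP Section 3.3 still states error control at 0.05 per cohort, and one sentence would settle the matter.

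The factual part stands: the source is not given, and a reader cannot tell whether 40% and 30% are doublet, monotherapy or discounted rates. The charge of contradiction does not stand. Results from an earlier study are historical data, so Sections 1.5.1 and 9.2.3 are compatible. Section 1.5.1 links approximate stage sizes to that study without saying that p0 equals its rate; only the melanoma paragraph names a figure to beat. The Synopsis phrase gives no rate. The reported rates are also imperfect benchmarks for an untreated population: the RCC figure mixes 0 and 1 prior line in 19 subjects, and the UC figure is not split by line. Round planning values near such estimates are ordinary design judgment.

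**Conclusion.** This is a missing citation for two planning values, and it calls for no change. The tabled designs do what they claim at their own rates: error 0.048 and 0.046, power 0.851 and 0.853. The inflation to about 25% (RCC) and 14% (UC) arises only if small, preliminary point estimates are taken as the true doublet rates in the Phase 2 population. The intervals do not establish that, and they do not exclude 40% or 30%.

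The remaining efficacy output is a descriptive ORR from a study that stopped enrolling early. It would be the same whatever source was named, because no stopping rule, test or promising/nonpromising call will be made against p0. The judgment would differ if the Simon decisions were still to be taken: the meaning of the 0.05 error in RCC and UC would then depend on where 40% and 30% came from.

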9.3. Level of Significance

For the primary efficacy endpoints, the 1-sided Type I error will be controlled at 0.05 for each individual cohort expansion. Note that this level of significance does not account for the multiple expansion cohorts. For other endpoints, confidence intervals will be reported at a 95% confidence level.

9.4. Statistical Analyses

9.4.1. Efficacy Analyses

9.4.1.1. Primary Efficacy Analyses

In Phase 2, ORR, defined as the percentage of subjects having CR or PR per RECIST v1.1 will be summarized by tumor type. For CPI-naïve melanoma subjects, CRR, defined as the percentage of subjects who have a CR per RECIST v1.1, will be summarized.

9.4.1.2. Secondary Efficacy Analyses

Disease control rate, defined as the percentage of subjects having CR, PR, or SD, as per RECIST v1.1 and mRECIST.

Progression-free survival, DOR, and duration of disease control (CR, PR, and SD) will be estimated using the Kaplan-Meier method as per RECIST v1.1 and mRECIST. Overall survival will be estimated using the Kaplan-Meier method.

In Phase 2, ORR, defined as the percentage of subjects having CR or PR per RECIST v1.1 and mRECIST will be summarized by tumor type.

9.4.2. Safety Analyses

9.4.2.1. Adverse Events

A TEAE is any AE either reported for the first time or worsening of a pre-existing event after the first dose of study treatment. Analysis of AEs will be limited to TEAEs, but data listings will include all AEs regardless of their timing to study treatment administration. Adverse events will be tabulated by the MedDRA preferred term and system organ class. Severity of AEs will be based on the CTCAE v4.03, using Grades 1 through 5.

The subset of AEs considered by the investigator to have a relationship to study treatment will be considered to be treatment-related AEs. If the investigator does not specify the relationship of the AE to study treatment, the AE will be considered treatment-related. The incidences of AEs and treatment-related AEs will be tabulated.

9.4.2.2. Clinical Laboratory Tests

Laboratory test values outside of the normal range will be assessed for severity based on the normal ranges for the clinical reference laboratory. The incidence of abnormal laboratory values and shift tables relative to baseline will be tabulated.

Laboratory data will be classified into Grades 1 through 4 using CTCAE v4.03. The following summaries will be produced for the laboratory data:

- Number and percentage of subjects with worst postbaseline CTCAE grade (regardless of baseline value). Each subject will be counted only for the worst grade observed postbaseline.
- Shift tables from baseline to the worst postbaseline value using CTCAE grade.

- For laboratory parameters where CTCAE grades are not defined, shift tables to the worst postbaseline value using the low/normal/high classifications based on laboratory reference ranges.

9.4.2.3. Vital Signs

Descriptive statistics and mean change from baseline will be determined for vital signs (blood pressure, pulse, respiratory rate, body temperature, and pulse oximetry) at each assessment time. Vital sign results will be reviewed for clinically notable abnormalities (see Table 22), and subjects exhibiting clinically notable vital sign abnormalities will be listed. A value will be considered an "alert" value if it is outside the established range and shows a > 25% change from baseline.

Table 22: Criteria for Clinically Notable Vital Sign Abnormalities

Parameter	High Threshold	Low Threshold
Systolic blood pressure	> 155 mmHg	< 85 mmHg
Diastolic blood pressure	> 100 mmHg	< 40 mmHg
Pulse	> 100 bpm	< 45 bpm
Temperature	> 38°C	< 35.5°C
Respiratory rate	> 24/min	< 8/min

9.4.2.4. Electrocardiograms

Descriptive statistics and mean change from baseline will be determined for each ECG parameter at each assessment time. Electrocardiogram results will be reviewed for clinically notable abnormalities according to predefined criteria (see Table 23). Subjects exhibiting clinically notable ECG abnormalities will be listed.

Table 23: Criteria for Clinically Notable Electrocardiogram Abnormalities

Parameter	High Threshold	Low Threshold
QTcF	> 460 msec	< 295 msec
PR	> 220 msec	< 75 msec
QRS	> 120 msec	< 50 msec
QT	> 500 msec	< 300 msec
RR	> 1330 msec	< 600 msec

QTcF = Fridericia correction.

[REDACTED]

[REDACTED]

9.5. Analyses for the Data Monitoring Committee

Formal safety reviews will be conducted by the study team (eg, medical monitor, clinical scientist, and biostatistician) and an independent internal review committee at least every 6 months, to review efficacy and safety data. Details regarding internal data monitoring will be addressed in the Data Monitoring Charter.

9.6. Interim Analysis

9.6.1. Simon 2-Stage Design

In Phase 2, the Simon 2-stage design will be applied for each tumor within a given treatment group (Simon 1989). During Stage 1, n_1 evaluable subjects treated at the recommended dose and schedule will be enrolled, and if r_1 or fewer responses are observed, then the cohort will be discontinued. As discussed in Section 9.2.3, the Simon 2-stage designs run for each tumor type within each treatment group will have design parameters that are determined by historical response rates and will have different sample sizes and different futility rules, depending on the historical response rate.

As an example, the probability of early termination for Stage 1 in the NSCLC tumor cohort for the triplet combination of INCAGN01876, pembrolizumab, and epacadostat is summarized in Table 24. If at least 4 responses are observed in the first evaluable 15 subjects, then 32 additional evaluable subjects would be enrolled in this cohort in Stage 2.

Table 24: Probability of Early Termination of Stage 1 for Simon 2-Stage Design

True Response Rate	Probability of Early Termination at Stage 1
15%	82.3%
20%	64.8%
25%	46.1%
30%	29.7%
35%	17.3%

9.6.2. Integrated Bayesian Futility Analysis

Treatment Groups C (concurrent dose administration) and D (run-in with INCAGN01876 × 1 dose followed by concurrent dose administration with immune therapies) represent different dosing strategies of the triplet combination of INCAGN01876, pembrolizumab, and epacadostat.

A second approach to determining whether the treatment is active or not across the cohorts will use an integrated Bayesian analysis of tumor and dosing strategies specific to Treatment Groups C and D based on Simon et al (2016). Pooling is performed within dosing strategies and tumor types to determine if INCAGN01876 is active within any of the given dosing strategies, given tumor types, or given dosing strategy-tumor type combinations. The first Bayesian pooling analysis will allow sharing of information within a tumor type across dosing strategies based on a joint Bayesian prior. The joint Bayesian prior incorporates the unacceptable and target response rates from the Simon 2-stage designs with a parameter indicating the prior probability of homogeneity within the tumor types, which controls the degree of information sharing. A separate analysis will allow sharing of information for dosing strategies across tumor types using a separate joint Bayesian prior. For this analysis, the joint Bayesian prior incorporates the unacceptable and target response rates from the Simon 2-stage designs with a parameter indicating the prior probability of homogeneity within the dosing strategies, which controls the degree of information sharing.

Each time a subject with the tumor type of interest is enrolled, 2 PoS calculations will be performed using the evaluable subjects: the PoS within tumor type (tumor type_i and dosing strategy_j), PoS_{1ij}, and PoS within dosing strategy (tumor type_i and dosing strategy_j), PoS_{2ij}.

Based on the results of the 2 calculated posterior PoS values, a tumor-sequence pair (i,j) will be considered open for enrollment if the maximum of PoS_{1ij} and PoS_{2ij} is greater than or equal to 20%. Otherwise the tumor-sequence pair will be suspended.

At the end of the study, overall PoS tests will be performed using both PoS_{1ij} and PoS_{2ij}. A tumor-sequence strategy will be considered successful if either PoS_{1ij} or PoS_{2ij} is > 80%.

10. ETHICAL CONSIDERATIONS AND ADMINISTRATIVE PROCEDURES

10.1. Investigator Responsibilities

This study will be performed in accordance with ethical principles that originate in the Declaration of Helsinki and conducted in adherence to the study Protocol; GCPs as defined in Title 21 of the US CFR Parts 11, 50, 54, 56, and 312; ICH E6 GCP consolidated guidelines; and local regulatory requirements as applicable to the study locations.

The investigator will be responsible for:

- Permitting study-related monitoring, sponsor audits, IRB/IEC review, and regulatory inspections by providing direct access to source data and other relevant clinical study documents.
 - Monitoring: Qualified representatives of the sponsor or its designee, study monitors, will monitor the study according to a predetermined plan. The investigator must allow the study monitors to review any study materials and subject records at each monitoring visit.
 - Auditing: Qualified representatives of the sponsor or its designee may audit the clinical study site and study data to evaluate compliance with the Protocol, applicable local clinical study regulations, and overall study conduct. The investigator must allow the auditors to review original source records and study documentation for all subjects.
 - Regulatory inspection: Regulatory authorities may conduct an inspection of the study and the site at any time during the development of an investigational product. The investigator and staff are expected to cooperate with the inspectors and allow access to all source documents supporting the eCRFs and other study-related documents. The investigator must immediately notify the sponsor when contacted by any regulatory authority for the purposes of conducting an inspection.
- Obtaining informed consent and ensuring that the study subjects' questions have been answered and the subjects fully understand study procedures:
 - Informed consent must be obtained before any study-related procedures are conducted, unless otherwise specified by the Protocol.
 - Informed consent must be obtained using the IRB/IEC-approved version in a language that is native and understandable to the subject. A template will be provided by the sponsor or its designee. The sponsor or its designee must review and acknowledge the site-specific changes to the ICF template. The ICF must include a statement that the sponsor or its designee and regulatory authorities have direct access to subject records.

- Obtaining approval from the IRB/IEC before the start of the study and for any changes to the clinical study Protocol, important Protocol deviations, routine updates, and safety information in accordance with institutional requirements and local law.
 - The investigator is responsible for ensuring that the safety reports provided by the sponsor are reviewed and processed in accordance with regulatory requirements and with the policies and procedures established by the IRB/IEC.
- Adhering to the Protocol as described in this document and agreeing that changes to the Protocol procedures, with the exception of medical emergencies, must be discussed and approved, first, by the sponsor or its designee and, second, by the IRB/IEC. Each investigator is responsible for enrolling subjects who have met the specified eligibility criteria.
- Retaining records in accordance with all local, national, and regulatory laws, but for a minimum period of at least 2 years after the last marketing application approval in an ICH region and until there are no pending or contemplated marketing applications in an ICH region, or if not approved, 2 years after the termination of the test article for investigation to ensure the availability of study documentation should it become necessary for the sponsor or a regulatory authority to review.
 - The investigator must not destroy any records associated with the study without receiving approval from the sponsor. The investigator must notify the sponsor or its designee in the event of accidental loss or destruction of any study records. If the investigator leaves the institution where the study was conducted, the sponsor or its designee must be contacted to arrange alternative record storage options.
 - All eCRF data entered by the site (including audit trail), as well as computer hardware and software (for accessing the data), will be maintained or made available at the site in compliance with applicable record retention regulations. The sponsor will retain the original eCRF data and audit trail.

